10.5.4 Exposure to Study Drug

Descriptive statistics (n, mean, standard deviation, median, and range) will be used to summarize:

- Duration of exposure (the interval between first dose date and last dose date)
- Actual cumulative dose (the total dose administered during the drug exposure period)
- Average daily dose (the ratio of total dose administered and treatment duration)
- Relative dose intensities (the ratio of the actual cumulative dose to the planned cumulative dose through the drug exposure period)

Dose withholding is defined as missing dose for \geq 7 consecutive days. Dose reduction is defined as taking lower dose level (100 mg QD) for \geq 3 consecutive days. Number of subjects with dose withholding and dose reduction will be summarized.

10.6 Analyses of Efficacy Endpoints

10.6.1 Primary Endpoint - Overall Response

10.6.1.1 Definition

ORR is defined as the proportion of subjects achieving either PR or CR as best overall response according to the Lugano classification as assessed by investigators.

10.6.1.2 Analysis Methods

The primary analysis of ORR will be conducted on the All-treated Population. ORR and the corresponding 95% two-sided CI calculated using the exact binomial distribution will be presented. Subgroup analysis per Section 6.2 will be provided.

The order of overall response category is: CR > PR > SD > PD. Descriptive statistics will be provided for best overall response. The number and proportion of subjects within each category of response as well as the associated 95% Cls will be presented. The proportion will be estimated by dividing the number of subjects within each category of response by the total number of subjects in the analysis population. Each subject will be counted within only one response group, with the best response during the study as the classification group.

10.6.2 Secondary Endpoints

10.6.2.1 **Definition**

10.6.2.1.1 Duration of Response

Acalabrutinib (ACE-LY-004)
Date: 15 March 2017

Statistical Analysis Plan

DOR is defined as the interval from the first documentation of CR or PR to the earlier of the first documentation of objective MCL disease progression or death from any cause. Subjects not meeting the criteria and alive by the analysis data cutoff date will be censored and the detail censoring rules for DOR are summarized in Appendix13.3.

10.6.2.1.2 Progression-free Survival

PFS is defined as the interval from the start of acalabrutinib therapy to the earlier of the first documentation of objective MCL disease progression or death from any cause. Subjects not meeting the criteria and alive by the analysis data cutoff date will be censored and the detail censoring rules for primary and sensitivity analyses of PFS are summarized Appendix 13.4.

10.6.2.1.3 Overall Survival

The duration of OS will be measured from the time of first study drug administration until the date of death from any cause. Subjects who are known to be alive as of their last known status will be censored at their last date known to be alive. The detail censoring rules for OS are summarized Appendix 13.5.

10.6.2.1.4 IRC-assessed Endpoints per Lugano Classification

[figure not shown]
ORR, DOR, and PFS assessed by the IRC per Lugano classification are defined similarly as those assessed by the investigator.

10.6.3 Analysis Methods

The analysis of DOR will be conducted on the subset of the All-treated Population who achieve CR or PR as their best overall response. The analysis of PFS and OS will be conducted on the All-treated Population. The analysis of DOR, PFS, and OS will be estimated using the Kaplan-Meier (KM) method. KM estimates with 95% CIs will be calculated for event time quartiles, and event-free rates will be calculated at selected timepoints. In addition, the reason for censoring will be summarized for DOR, PFS, and OS. The same analysis methods for investigator-assessed ORR will be applied to IRC-assessed ORR. The discordant responses assessed by the investigator and IRC using the Lugano classification will be provided.

[figure not shown]
10.6.4 Exploratory Analyses

10.6.4.1 CCI

10.7 Analyses Safety Endpoints

Safety analyses will be performed on the All-treated Population.

10.7.1 Adverse Events

The Medical Dictionary for Regulatory Activities (MedDRA Version 19.1) will be used to code all AEs to a system organ class and a preferred term. The severity of the AE will be assessed by National Cancer Institute (NCI) Common Terminology Criteria for Adverse Events (CTCAE) Version 4.03. Study drug-related AEs are those assessed by investigator as related.

Treatment-emergent AEs are defined as those events that occur or worsen on or after the first dose of study drug, through the treatment phase, and within 30 days following the last dose of study drug.

Treatment-emergent AEs will be summarized by system organ class and preferred terms in descending order of frequency, by CTCAE toxicity grade. Drug-related treatment-emergent AEs, serious treatment-emergent AEs and drug-related serious treatment-emergent AEs, treatment-emergent AEs leading to treatment discontinuation, dose delay and dose modification will be summarized by preferred teams in descending order of frequency and by CTCAE toxicity grade.

Death information is reported in the study exit CRF for all deaths. Incidences of deaths are to be reported, along with the primary cause of death.

Acerta Pharma Confidential Page 18 of 28

10.7.2 Adverse Events of Clinical Interest

Adverse events of clinical interest (ECI) corresponding search strategy are defined in Appendix B of the SAP for the acalabrutinib Integrated Summary of Safety (ISS).

Subject incidence rates of ECIs will be tabulated using the CTCAE Version 4.03.

10.7.3 Laboratory Test Results

Laboratory data of hematology, serum chemistry, serum immunoglobulin, and T/B/NK cell counts up to 30 days after last dose or the safety follow-up visit date, whichever is later, will be reported in SI units. Applicable laboratory results will be graded according to CTCAE Version 4.03. Generic normal ranges specified in American Medical Association (AMA) Manual of Style 10th Edition (2017) will be applied whenever reference ranges are not available.

Shift from baseline to the worst grade during the treatment will be provided as shift tables for selected parameters. Figures of selected parameters will be plotted overtime as appropriate.

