3.6 CONCOMITANT THERAPY

3.6.1 Permitted Concomitant Therapy

Antiemetics are permitted if clinically indicated. Standard supportive care medications are permitted as per institutional standards.

For subjects considered at risk for tumor lysis syndrome: Administer appropriate hydration and allopurinol or rasburicase per institutional standards before initiating treatment.

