3.6.4 Prohibited Concomitant Therapy

Any chemotherapy, anticancer immunotherapy, corticosteroids (at dosages equivalent to prednisone > 10 mg/day), experimental therapy, or radiotherapy for treating MCL are prohibited.

Localized, short courses of radiotherapy are allowed for the treatment of lesions unrelated to the disease under study, if approved by the medical monitor.

Warfarin or equivalent vitamin K antagonists (eg, phenprocoumon) are prohibited.

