4.1.4 Concomitant Medications and Therapy

Document all concomitant medications and procedures from within 21 days before the start of study drug administration through 30 days after the last dose of study drug.

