4.1.16 Serum Immunoglobulin

Testing for immunoglobulin G (IgG), IgM, and IgA will be done by the central laboratory.

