- Women of childbearing potential only. Urine pregnancy tests will be performed at Screening, on Cycle 1 Day 1; on Day 28 of Cycles 1-12; on Day 28 of Cycles 15, 18, 21, and 24, then every 24 weeks; and at the early termination or safety follow-up visit. Testing will be done locally by use of central laboratory-provided kits. Pregnancy testing may be done by local laboratories and can be done more frequently than the protocol-defined schedule, if required by local regulatory authorities.

- h. Hematology includes complete blood count with differential and platelet counts. Cycle 1 Day 1 hematology does not need to be repeated if screening hematology was within 5 days.
- i. Serum chemistry: albumin, alkaline phosphatase, alanine transaminase (ALT), aspartate aminotransferase (AST), bicarbonate, blood urea nitrogen (BUN), bone-specific alkaline phosphatase, calcium, chloride, creatinine, c-terminal telopeptide, glucose, lactate dehydrogenase (LDH), magnesium, phosphate/phosphorus, potassium, sodium, total bilirubin, total protein, and uric acid. Cycle 1 Day 1 serum chemistry does not need to be repeated if screening chemistry was within 5 days.
- j. Urinalysis: pH, ketones, specific gravity, bilirubin, protein, blood, and glucose.
- k. T/B/NK cell count (ie, CD3, CD4, CD8, CD19, CD16/56). During Cycles ≥ 5 , only done at the end of Cycles 6, 12, 18, and 24, then every 24 weeks thereafter.
- l. Serum immunoglobulin: IgG, IgM, IgA. During Cycles ≥ 5 , only done at the end of Cycles 6, 12, 18, and 24, then every 24 weeks thereafter.
- m. Pharmacodynamic (PD) assessments will be done on up to 24 bortezomib-naive subjects and up to 24 bortezomib-exposed subjects. PD samples are drawn predose and 4 hours (± 10 minutes) postdose on the days indicated (relative to the morning dose).
- n. Pharmacodynamic (PD) assessments will be done on up to 24 bortezomib-naive subjects and up to 24 bortezomib-exposed subjects. PD samples are drawn predose on the days indicated
- o. Pharmacokinetic (PK) assessments will be done on up to 24 bortezomib-naive subjects and up to 24 bortezomib-exposed subjects. PK samples are drawn per [Table 4-1](#), and timepoints are relative to the morning dose.
- p. Bone marrow are required for confirmation of CR (if bone marrow was involved by lymphoma at baseline) per clinical guidelines (see [Section 4.2](#)).

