4.2.2 Safety

- Frequency and severity of AEs/SAEs
- Frequency of AEs requiring discontinuation of study drug or dose reductions
- Effect of acalabrutinib on peripheral T/B/natural killer (NK) cell counts
- Effect of acalabrutinib on serum immunoglobulin levels

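### SAP 10.7.3 does not separate IgG values drawn after immunoglobulin replacement, so replacement started on study can make IgG summaries understate a fall

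*SAP*

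**What the plan says.** SAP section 4.2.2 lists "Effect of acalabrutinib on serum immunoglobulin levels" as a secondary safety endpoint. Protocol section 4.1.16 defines the measurement: "Testing for immunoglobulin G (IgG), IgM, and IgA will be done by the central laboratory".

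The analysis text is SAP section 10.7.3. It takes in "Laboratory data of hematology, serum chemistry, serum immunoglobulin, and T/B/NK cell counts up to 30 days after last dose", or to the safety follow-up visit if that is later, and makes no exception. It then says "Shift from baseline to the worst grade during the treatment will be provided as shift tables for selected parameters", and that selected parameters will be plotted over time. It does not say whether immunoglobulins are among the selected parameters. Protocol section 5.5.4 plans figures of laboratory changes over time without that restriction.

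Immunoglobulin replacement is not named in either document. Protocol section 3.6.1 says "Standard supportive care medications are permitted as per institutional standards". The prohibited list in section 3.6.4 does not reach it: "Any chemotherapy, anticancer immunotherapy, corticosteroids (at dosages equivalent to prednisone > 10 mg/day), experimental therapy, or radiotherapy for treating MCL are prohibited".

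Immunoglobulins are sampled on Cycle 1 Day 1 and at the end of Cycle 2; from Cycle 5 they are "only done at the end of Cycles 6, 12, 18, and 24, then every 24 weeks thereafter", with a further sample at early termination or safety follow-up. The data needed to identify replacement are collected. Protocol section 4.1.4 says "Document all concomitant medications and procedures from within 21 days before the start of study drug administration", and recording continues to 30 days after the last dose.

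**The concern.** A total IgG result cannot be split into what the subject made and what was infused. Once replacement starts, the measured value no longer isolates what happened to the subject's own IgG, which is what the endpoint asks about.

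Replacement begun during the study would tend to go to subjects with low IgG or infections. Their later values rise and pull the group summary toward no effect. Protocol section 3.7.1 names serious infection, including fatal cases, as a risk of the drug, so an understated fall in IgG is the less safe error. The trial has no comparator to absorb it. From Cycle 6 the scheduled samples are about 24 weeks apart, so a fall can also be found locally and treated before the next central sample.

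**Working it through.** Neither document gives an IgG figure to reproduce, and the ORR power calculation does not bear on this point. The check is a reading of the text followed by illustrative arithmetic.

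**1. Is there a rule?** SAP 10.7.3 sets a time window and units and makes no exception for replacement. It shows no redaction that could hide one. SAP 10.5.2 summarises concomitant medications but does not link them to the IgG data. Protocol 5.4 limits imputation for safety data to dates.

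**2. Effect on one subject.** Let *r* be the infused contribution to a sample. Then

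observed change = true change + (*r* at the visit − *r* at baseline).

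- Replacement started on study: *r* at baseline is 0 and *r* at the visit is positive, so the fall is understated.
- Replacement at baseline, then stopped: the fall is overstated.
- Replacement continued unchanged: the two terms roughly cancel in g/L.

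**3. Effect on a visit mean.** For replacement started on study, bias = share replaced × rise. Both inputs are assumptions.

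| Share replaced | Rise 2 g/L | Rise 9 g/L |
|---|---|---|
| 5% | 0.10 | 0.45 |
| 10% | 0.20 | 0.90 |
| 20% | 0.40 | 1.80 |

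**4. Simulation, all inputs assumed.** 117 subjects, 2,000 repeats. Baseline IgG has mean 7 and SD 3 g/L. A mean true fall of about 25% accrues by Cycle 24. After any scheduled value below 4 g/L, replacement starts with probability 10% to 60% and raises later values by 3 or 5 g/L. Results at Cycle 24 are means of individual percent changes.

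| Start probability, rise | Replaced | True | All values | Post-replacement set aside |
|---|---|---|---|---|
| 10%, 3 g/L | 7.2% | −24.8% | −19.0% | −24.2% |
| 30%, 3 g/L | 17.6% | −24.8% | −10.9% | −23.3% |
| 30%, 5 g/L | 17.8% | −24.8% | −1.4% | −23.3% |
| 60%, 5 g/L | 26.1% | −24.7% | +8.5% | −22.0% |

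The percent scale enlarges the effect, because replaced subjects tend to have low baselines. In the last row the shift in g/L is 0.261 × 5 = 1.3, or 1.3/7 = 19% of the baseline mean, against 33 points on the percent scale.

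**5. Worst-value summaries.** In the same four rows:

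- Below 4 g/L at Cycle 24: a true share of about 37% to 38% is observed as 31%, 21%, 21% and 13%.
- Below 4 g/L at any visit: 40% in truth and as observed. This follows from the set-up, in which replacement starts only after a low sample has been recorded.
- Fall of more than 50% at the worst visit: a true 11% is observed as 9.9%, 8.2%, 8.1% and 6.4%. At Cycle 24 alone it is observed as 9.8%, 7.8%, 7.7% and 5.8%.

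A low value already sampled is kept. A fall that deepens after replacement starts is still hidden in part.

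**The case against.** The strongest reply is that SAP 10.7.3 does not promise a mean change in IgG at all. It specifies shifts to worst grade and figures, both for selected parameters, and the sentence on immunoglobulins only sets a reporting window. That post-replacement values enter the summaries is inferred from the absence of an exception. This stands as a limit, but the general descriptive text in SAP 10.1 and the figures in Protocol 5.5.4 leave means and time plots within the plan.

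Second, nothing shows that anyone received replacement, and every input on size is assumed. That stands in full.

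Third, part of the need is met already. SAP 10.5.2 would list replacement products among concomitant medications, infections are captured as adverse events, and IgM and IgA are measured. That helps, but the medication table does not separate new starts from continuing use, and none of it corrects an IgG plot.

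Fourth, the endpoint is descriptive, SAP section 5 tests no formal hypotheses, and no decision rule uses IgG. That also stands and keeps the point minor.

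A reader might go further and infer that later samples measure only infused IgG, that the largest falls disappear, or that the error can run in only one direction. The documents do not support these. Total IgG includes the subject's own, a low value sampled before replacement remains in the data, and no eligibility criterion names replacement, so a raised baseline is possible.

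**Conclusion.** The gap is real and minor. As written, the plan would mix infused with endogenous IgG in a single-arm assessment of a secondary safety endpoint. Replacement started on study would tend to make visit means, time plots and last values understate a fall. Worst-value summaries are affected less, and replacement at baseline can push the change either way.

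The size is unknown. The range of 0.10 to 1.8 g/L rests on an assumed 5% to 20% of subjects replaced and an assumed rise of 2 to 9 g/L; its upper end multiplies two chosen extremes. The simulation shows that a material distortion is possible under its assumptions, not that one occurred. It would be wrong to conclude that the trial will report stable IgG while the drug lowers it: the documents give no replacement rate from which to say so.

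The argument concerns IgG. IgM and IgA are assumed to be little affected by replacement.

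**What to change.** In SAP section 10.7.3:

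- Use the concomitant-medication record to flag every IgG value drawn after any immunoglobulin replacement, including replacement before baseline.
- Show IgG change from baseline twice: with all values, and with post-replacement values set aside. Do not carry the last earlier value forward, which would conflict with the no-imputation statement in Protocol section 5.4.
- Report the number of subjects on replacement at baseline, and the number and timing of those starting it on study.
- Present IgM and IgA in full as supporting measures.

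The cost is SAP wording, one derived flag and one extra display. No new data are needed, since medications are already recorded and coded and partial dates have an imputation rule in SAP section 9.1.

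The downside is fewer IgG values at late visits and some remaining selection, because starting replacement is itself informative. In the simulation, setting values aside gave −24.2% to −22.0% against a true fall of about 25%, which removes most of the bias but not all. That is why both displays and the counts are needed. The flag also sees only what is recorded: replacement stopped more than 21 days before first dose, or given after day 30 but before a follow-up sample in the 7-day visit window, would be missed.

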10.7.3.1 Lymphocytosis

Lymphocytosis is defined as an elevation in absolute lymphocyte count (ALC) of \geq 50% compared to baseline and a post-baseline assessment >5x10 9 /L (Wang 2013). The number of subjects with at least one occurrence of lymphocytosis will be summarized. For subjects with lymphocytosis, resolution of lymphocytosis is defined as 1) a decrease of ALC value to the baseline level or lower, or 2) an achievement of ALC value that is below 5x10 9 /L, whichever occurs first. Duration of lymphocytosis (DOL) is defined as the duration of time from the earliest date on which the ALC value met the lymphocytosis criteria at a post-baseline assessment to the earliest date on which a subsequent ALC value met the resolution criteria.

DOL = Earliest date of meeting resolution criteria -Earliest date of meeting lymphocytosis criteria + 1.

Subjects who developed lymphocytosis but whose lymphocytosis was not resolved prior to the analysis cutoff date will be censored at the last sample date with non-missing ALC value at or prior to the analysis cutoff date.

Summary statistics will be provided for time to lymphocytosis. KM estimates for DOL will be provided.

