1.3 THERAPEUTIC OPTIONS FOR PREVIOUSLY-TREATED MANTLE CELL LYMPHOMA

BTK inhibition is a promising therapeutic intervention for the treatment of MCL. Ibrutinib, a first-in-class BTK inhibitor, has demonstrated substantial efficacy in patients with relapsed MCL based on data from a single-arm Phase 2 study of 111 patients (Wang 2013). In this study, which had an estimated median follow up of 15.3 months, the median PFS was 13.9 months (95% CI: 7.0-not reached [NR]) and ORR was 68% (CR: 21%; PR: 47%). The ORR was comparable between the bortezomib-naive and bortezomib-treated cohort of subjects, while median PFS was longer in the bortezomib-treated cohort (16.6 months) compared to the bortezomib-naive cohort (7.4 months).

The most frequently reported AEs in the study were diarrhea (50%, Grade 3: 6%), fatigue (41%, Grade 3: 5%), and nausea (31%, no Grade 3 AEs). Grade 3 and 4 hematologic AEs included neutropenia (in 16% of patients), thrombocytopenia (in 11%), and anemia (in 10%). Grade 3 bleeding AEs were reported in 5 patients, and 4 patients had subdural hematomas.

Other therapeutic agents that have received regulatory approval in relapsed MCL include bortezomib and lenalidomide. The ORR reported with both these agents is notably lower than that reported in the ibrutinib Phase 2 study. In a single arm, open-label study of lenalidomide in 134 patients with MCL who had relapsed after or were refractory to bortezomib (or a bortezomib-containing regimen), the ORR was 26% (1% CR) (REVLIMID® package insert). The efficacy of bortezomib was evaluated in a single-arm open label study of 155 patients with relapsed MCL (after at least 1 prior therapy); the ORR was 31% (6% CR).

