3 STUDY OVERVIEW

3.1 Study Design

This clinical trial is a phase 2, multicenter (approximately 70 global centers), open-label study in subjects with histologically documented MCL, who have relapsed after or were refractory to ≥1 (but not >5) prior treatment regimens. Subjects will be enrolled and will take 100 mg of acalabrutinib twice per day (bid) in repeated 28-day cycles.

Treatment with acalabrutinib may be continued until disease progression or an unacceptable drug-related toxicity, whichever occurs first. Dose modification provisions are provided in the study protocol. All subjects who discontinue study drug will have a safety follow-up visit 30 (+7) days after the last dose of acalabrutinib. An early

Acerta Pharma Confidential Page 6 of 28

termination visit is required for any subjects who permanently discontinued study drug for any reason including disease progression (exceptions included death, lost to followup, or withdrawal of consent).

All subjects will have hematology, chemistry, and urinalysis safety panels done at screening. Once dosing commences (Day 1), all subjects will be evaluated for safety, including serum chemistry and hematology, once weekly for the first 4 weeks, every 2 weeks in Cycle 2, every 4 weeks in Cycles 3 to 12, and every 12 weeks thereafter. PK/PD testing will be done in Cycles 1 and 2. Tumor assessments will be completed at 8- to 12-week intervals during the trial.

The primary efficacy analyses will be based on investigator assessment. An Independent Review Committee (IRC) will assess the efficacy endpoints in accordance with the IRC charter provided separately from this document.

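### Duration of lymphocytosis is to be estimated by plain Kaplan-Meier, with subjects who die unresolved censored at their last lymphocyte count; death should be a competing event and outcomes should be counted

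*SAP*

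**What the plan says.** SAP section 10.7.3.1 starts DOL at the first post-baseline absolute lymphocyte count (ALC) that meets the lymphocytosis criteria and ends it at "the earliest date on which a subsequent ALC value met the resolution criteria". Resolution is either "a decrease of ALC value to the baseline level or lower" or an ALC below 5x10^9/L, whichever comes first. Nothing restricts the resolving count to time on drug.

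One sentence covers unresolved subjects: "Subjects who developed lymphocytosis but whose lymphocytosis was not resolved prior to the analysis cutoff date will be censored at the last sample date". Death, end of treatment, withdrawal and loss to follow-up are not named, so they become censoring only through this general rule. On estimation the section says "KM estimates for DOL will be provided". The only count it plans is this: "The number of subjects with at least one occurrence of lymphocytosis will be summarized". It specifies no number or share resolved.

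Two other places matter. SAP section 10.7.3 reports laboratory data "up to 30 days after last dose or the safety follow-up visit date, whichever is later", so some counts after the last dose are used. SAP section 10.6.3 summarises reasons for censoring for DOR, PFS and OS, but not for DOL.

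**The concern.** KM is valid for time to resolution if a censored subject could still resolve and would do so at the same rate as those still followed. That is reasonable for a subject still being sampled at the data cutoff. It is wrong for a subject who died, because the chance of resolution after death is zero. Death before resolution is a competing event.

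Censoring such deaths has two consequences. The complement of the KM curve lies above the proportion who actually resolve by a given time. The KM quantiles of DOL are also shorter than the times at which the corresponding shares of subjects have resolved. The second does not depend on anyone reading the curve as a proportion.

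The planned output would not show this. With no count of subjects resolved or dead unresolved, and no table of censoring reasons for DOL, a reader of the KM estimates could not tell how many censored subjects could still have resolved.

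**Working it through.** The documents state no figure for DOL or for the share resolved, so there is none to reproduce.

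**Inputs from the documents.** The event, censoring rule and estimator come from SAP 10.7.3.1, and the laboratory window from SAP 10.7.3.

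**Assumptions.** The documents do not give this trial's number of subjects with lymphocytosis, time to resolution or death rate. I take constant hazards, a median time to resolution of 2, 6 or 12 months, and a median survival of 24 or 48 months.

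**Formulas.** Let a = ln 2 / median time to resolution and b = ln 2 / median survival.

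- With deaths censored: 1 - KM(t) = 1 - exp(-a t)
- With death competing: CIF(t) = a/(a+b) x [1 - exp(-(a+b) t)]
- Time at which half have resolved, on the cumulative-incidence scale: -ln(1 - 0.5(a+b)/a) / (a+b)

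**One cell in full** (resolution 6 months, survival 24 months, t = 12):

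- a = 0.1155, b = 0.0289, a+b = 0.1444
- 1 - KM = 1 - exp(-1.386) = 75.0%
- CIF = 0.8 x (1 - exp(-1.733)) = 0.8 x (1 - 0.1768) = 65.9%
- Gap = 9.1 points
- Half resolved: -ln(1 - 0.625)/0.1444 = 0.9808/0.1444 = 6.8 months, against a KM median of 6.0

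**All cells at 12 months, death alone competing:**

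| Median resolution (months) | Median survival (months) | 1 - KM | CIF | Gap (points) | KM median (months) | CIF-scale median (months) |
|---|---|---|---|---|---|---|
| 2 | 24 | 98.4% | 91.3% | 7.1 | 2.0 | 2.1 |
| 2 | 48 | 98.4% | 94.7% | 3.7 | 2.0 | 2.0 |
| 6 | 24 | 75.0% | 65.9% | 9.1 | 6.0 | 6.8 |
| 6 | 48 | 75.0% | 70.2% | 4.8 | 6.0 | 6.4 |
| 12 | 24 | 50.0% | 43.1% | 6.9 | 12.0 | 16.0 |
| 12 | 48 | 50.0% | 46.4% | 3.6 | 12.0 | 13.6 |

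The gap is 3.6 to 9.1 points. The median hardly moves when resolution is fast and moves by up to 4 months when it is slow.

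**End of treatment.** The SAP says "Treatment with acalabrutinib may be continued until disease progression or an unacceptable drug-related toxicity, whichever occurs first", so some subjects will stop drug unresolved. Their later counts, within the laboratory window, still count towards resolution, so stopping does not preclude the SAP's event. It mainly ends sampling soon afterwards. If subjects who stop differ from those who continue, the censoring is informative, but no passage says in which direction.

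**For contrast only.** Suppose the endpoint were resolution on treatment, with stopping or death competing at a median of 13.9 months. That is the median PFS quoted in Protocol section 1.3 for the ibrutinib study. The 12-month figures, 1 - KM against CIF, would be:

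- 98.4% against 86.7% (resolution median 2 months)
- 75.0% against 60.3% (6 months)
- 50.0% against 38.9% (12 months)

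That is a gap of 11 to 15 points, or 6 to 28 points over competing medians of 6 to 30 months. A simulation of 200,000 subjects gave 60.4% for the cell where the formula gives 60.3%. These figures belong to a different endpoint and do not size the present point.

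**The case against.** The strongest reply is that this is a descriptive laboratory summary in a single-arm study with no formal hypotheses (SAP section 5). The SAP promises KM estimates of a duration, not a proportion resolved. If resolution is fast, the median hardly changes: 2.0 against at most 2.1 months in the table. The size rests wholly on assumed rates. All of this stands and limits the point to a minor one. It does not remove the error in treating the dead as still able to resolve.

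A reader might infer three stronger things that the documents do not support.

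- **That stopping acalabrutinib is also a competing event.** This would hold only if the event were resolution on drug. The SAP's event is any later qualifying count, and its laboratory window runs past the last dose. Making every permanent discontinuation competing would discard resolutions that the SAP counts.
- **That the trial will report lymphocytosis as almost always transient.** No share resolved is planned, and 1 - KM need not approach 100% when the longest follow-up times are censored.
- **That unresolved subjects who stop or die are those with the worst prognosis.** No passage links persistence of lymphocytosis to progression or death.

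**Conclusion.** The point holds for death. The direction is certain: where deaths occur before resolution, 1 - KM overstates the cumulative incidence of resolution and KM quantiles of DOL are too short on that scale. The size is about 4 to 9 points at 12 months. That assumes constant hazards, median survival of 24 to 48 months, median time to resolution of 2 to 12 months, and deaths occurring at that rate while counts are still being taken. If most deaths come after sampling has ended, the part due to death is smaller. The actual size cannot be computed from the documents.

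For end of treatment the finding is weaker: potentially informative censoring of unknown direction. The reporting gap is clear in either case, because DOL is left out of the summary of censoring reasons. This is a cheap improvement. It does not touch ORR, DOR, PFS or OS.

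**What to change.** In SAP section 10.7.3.1:

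1. Report the cumulative incidence of resolution at fixed times by the Aalen-Johansen method, with death before resolution as the competing event. State that deaths are counted while the subject is within the laboratory window of section 10.7.3, since resolution cannot be seen after it.
2. Continue to censor all other unresolved subjects at the last ALC. Say explicitly that this includes withdrawal of consent and loss to follow-up.
3. Tabulate the numbers resolved; died unresolved; with ALC sampling ended unresolved after treatment stopped, by reason; withdrawn or lost unresolved; and ongoing at cutoff.
4. Keep the KM estimates of DOL as a supplementary output.
5. If resolution on treatment is of interest, treat permanent discontinuation as competing only in an optional sensitivity analysis labelled as on-treatment resolution.

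The cost is a short SAP edit and one extra table, from data already collected. The resolution figure may look slightly less favourable.
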